## ***5.5. Primary and Secondary Outcome Measures***

Outcome rate will be assessed at the end of the intervention period in all hospitals (data collection period III) (Table 4).

### ***5.5.1. Primary outcomes***

- Episiotomy rate:

Number of episiotomies among single vaginal deliveries.

- Active management of third stage of labor:

Number of women who received injections of 10 International Units of oxytocin during third stage of labor, among single vaginal deliveries.

### ***5.5.2. Secondary outcomes***

#### ***5.5.2.1. Clinical secondary outcomes***

- Perineal sutures:

Number of women with at least one perineal suture among single vaginal deliveries.

- Postpartum hemorrhage >500ml:

Number of women with measured total blood loss >500ml among single vaginal deliveries

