## ***2.4.Secondary outcomes***

### *2.4.1. Clinical secondary outcomes*

- Perineal sutures rate among single vaginal deliveries.
- Incidence of postpartum hemorrhage >500ml among single vaginal deliveries.

Perineal sutures and hemorrhages will be studied to estimate the health impact of the intervention. Previous studies have established that selective use of episiotomy decreases the frequency of perineal sutures and that active management of the third stage of labor decreases hemorrhages. However, we will measure the effectiveness of their use in the context of our study.

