## ***5.4. Collection of Biological Samples***

### ***5.4.1. Measured total blood loss (ml)***

Nurses, midwives and physicians who are a part of the teams attending deliveries at participating hospitals will be trained in post-partum blood loss measurement. Nurses and midwives will be the main persons responsible for the measurements. Both the country coordinators and the data collection supervisors will be in charge of training. A pilot study will be implemented at the pilot hospital in Montevideo (Pereira Rossell) to assess the acceptability of the measuring technique.

Measurement technique:

A plastic bag designed to collect blood (drape) will be used to collect post-partum blood loss. The drape is made of transparent plastic and will not be calibrated.

As soon as the baby is delivered, the drape is placed under the buttock. The blood is allowed to collect into the drape as long as the woman stays in the delivery bed or chair. The time of delivery and the time when the blood collection starts and finishes will be recorded. At the end of the blood collection period, the amount of blood loss will be measured by weighing the drape on a scale provided by the study and translating g to ml. The blood and collection drape will be properly disposed of once weighed and the amount of blood loss will be recorded in the CLIN1 form by the birth attendant or the nurse.

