### ***6.3. Training of Biological Sample Collectors***

Nurses or midwives in the labor ward of each hospital will be trained in how to measure total blood loss in vaginal deliveries. They will be trained to perform this measurement as a routine activity in all vaginal deliveries during the data collection periods. Data supervisors and Country coordinators will be in charge of the training activities and will provide hospitals with the standard measuring drapes.

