Project clinical outcomes include the primary and secondary clinical outcomes for the study (e.g., episiotomy rate and active management during the third stage of labor). The instruments for data collection are the clinical data collection forms (CLIN1, ALTA1, CLIN2 and ALTA2) (Appendix 6). The only difference between the two forms is that CLIN2 contains blood loss in milliliters (see Appendix 6 for data collection forms.)

**Bias minimization:** Data on outcomes will be collected for all the hospitals in the study (24 hospitals). The data collection system for outcomes will be independent from the implementation of the intervention. Given the nature of the intervention, we cannot blind the randomization, and data collectors will know if they belong to an intervention/control hospital. Furthermore, intervention hospitals will receive a computer to implement the intervention, which will be used, among other things, to monitor clinical data (i.e., episiotomy rate and active management of the third stage of labor). As a consequence, it is expected that the intervention will improve the capacity of intervention hospitals to collect and review clinical data and bias might be introduced in outcome assessment. To minimize this problem, the data collection system will be isolated from the intervention instruments as much as possible. In practical terms, this means that data collectors at the hospital level, data supervisors and computer hardware for data collection will have no role associated with intervention activities.

**Data sources and data collection forms:** Figure 3 presents a summary of the proposed system for data collection. All hospitals in the project currently use a standard clinical record (PIS form) developed by CLAP. This is a paper form that registers data on obstetric history, antenatal care, labor, delivery, and neonatal outcomes. Additional information is recorded in

other instruments depending on the hospital (i.e. laboratory results, ultrasound results, etc.). Because PIS is the clinical record, the form is completed for all women, and data is recorded during hospital admission, labor, delivery, and discharge from hospital. This form was developed by CLAP in 1984 as part of technical cooperation provided by the center to countries in Latin America and the Caribbean. Some, but not all, of the hospitals in the study enter the data in the PIS paper form in computer format using a program that was developed by CLAP.

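### Postpartum hemorrhage is defined with a measured-only numerator over all single vaginal deliveries and no fixed collection time, so unmeasured women score as non-cases and any difference in completeness between arms can bias the comparison.

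*Protocol*

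**What the plan says.** Section 5.5.2.1 of the protocol gives the outcome as "Number of women with measured total blood loss >500ml among single vaginal deliveries". Section 2.4.1 names the same outcome without requiring a measurement: "Incidence of postpartum hemorrhage >500ml among single vaginal deliveries". The two agree only if every delivery is measured.

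Section 5.4.1 describes the measurement. On duration it says: "The blood is allowed to collect into the drape as long as the woman stays in the delivery bed or chair". No minimum or fixed period is given. It adds that "The time of delivery and the time when the blood collection starts and finishes will be recorded", but the outcome definition does not use these times. The drape is weighed, and "the amount of blood loss will be recorded in the CLIN1 form by the birth attendant or the nurse".

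Section 6.3 sets the intended coverage: staff are to be "trained to perform this measurement as a routine activity in all vaginal deliveries during the data collection periods". Section 9.1 accepts that allocation cannot be blinded, that "data collectors will know if they belong to an intervention/control hospital", and that "bias might be introduced in outcome assessment".

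**The concern.** The numerator is conditional on a measurement and the denominator is not. A woman whose drape was not used, or not weighed, cannot be counted as a hemorrhage but is still counted as a delivery. In effect she is scored as having had none.

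The open collection time acts in the same direction for a different group: women at or below 500 ml when collection ends who go on to lose more.

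Hemorrhage is one of two clinical secondary outcomes chosen to show whether the practice change affects health (section 2.4.1), and it appears in a main research question (section 2.2). If completeness or time in bed differed between arms, part of any observed difference would reflect measurement. A difference in time in bed is conceivable, because the intervention targets third-stage management itself.

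**Working it through.** **The plan's own figures.** Section 10.3 assumes a 15% hemorrhage rate, an SD of 5% between hospitals and 9 hospitals per arm. With a two-sided 0.05 level (the sidedness is my assumption) and the normal approximation, the standard error of the difference is 5 × √(2/9) = 2.357 points.

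- 15% to 8%: 7/2.357 = 2.970; Φ(2.970 − 1.960) = 84.4%. Stated: 84%.
- 15% to 10%: 5/2.357 = 2.121; Φ(2.121 − 1.960) = 56.4%. Stated: 56%.

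Both reproduce, so no stated number is in dispute. The calculation takes the rate as fully observed.

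**Effect of unmeasured deliveries.** Let c be the share of deliveries with a drape weight. If missingness is unrelated to bleeding, the definition reports true rate × c. The protocol gives no value for c, so those below are assumptions.

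| Share measured (c) | Reported when the true rate is 15% |
|---|---|
| 95% | 14.25% |
| 90% | 13.5% |
| 80% | 12.0% |
| 75% | 11.25% |
| 70% | 10.5% |

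**Equal shortfall in both arms.** At c = 90%, a true 15% v 8% is reported as 13.5% v 7.2%. The ratio is unchanged (8/15 = 7.2/13.5 = 0.533) and the difference shrinks from 7 to 6.3 points. If both arms are truly 15%, both report 13.5% and no spurious difference arises.

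**Unequal shortfall, no true effect (15% in both arms).** The last two columns give the rejection probability of the two-sided 5% t-test on follow-up percentages. They come from the noncentral t with noncentrality (shift/5) × √(n/2) and 2n − 2 degrees of freedom, for n hospitals per arm. For a shift of 2.25 and n = 12, the noncentrality is 0.45 × √6 = 1.10.

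| c in the two arms | Reported | Spurious shift | n = 12 | n = 9 |
|---|---|---|---|---|
| 90% v 80% | 13.5% v 12.0% | 1.5 points | 10.8% | 9.2% |
| 90% v 75% | 13.5% v 11.25% | 2.25 points | 18.4% | 14.6% |
| 90% v 70% | 13.5% v 10.5% | 3.0 points | 29.0% | 22.4% |

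The sign depends on which arm measures less. Fewer measurements in the intervention arm look like benefit; fewer in the control arm look like harm.

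**Missingness related to bleeding.** Suppose (assumed) a true rate of 15%, 10% unmeasured, and hemorrhage in half of those. Per 100 deliveries there are 15 cases, 5 of them unmeasured and 10 measured. The present definition gives 10/100 = 10.0%. A measured-only denominator gives 10/90 = 11.1%. Neither recovers 15%.

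**General form.** With rate p among measured women and assumed rate r among unmeasured women, the overall rate is c × p + (1 − c) × r. The present definition is the case r = 0. With c = 90% and p = 15%, r = 0 gives 13.5%, r = 15% gives 15.0% and r = 50% gives 18.5%.

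**The case against.** The best case for the plan has five parts.

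- *No rule codes missing as no hemorrhage.* All four clinical outcomes use the same population phrase, and the word measured may only name the method. Handling of missing values may sit in an analysis plan that is not shown. This is fair as to intent. But section 5.5.2.1 is a written definition with both parts of the fraction, and followed literally it scores unmeasured women as non-cases.
- *Completeness is well protected.* Measurement is planned for all vaginal deliveries (6.3), required fields are checked at entry (9.3), missing data are reported by hospital (9.9.1, 9.9.3), and data collectors at poorly performing hospitals may be retrained (6.7). These steps make missing values fewer. They do not change how a missing value is scored.
- *Section 9.1 speaks of data collectors, not those who weigh the drape.* Correct: section 6.1 makes them data-entry staff, and a scale weight leaves less room for judgment than a visual estimate. Still, birth attendants or nurses record the loss, birth attendants are the target of the intervention, and the isolation measures in section 9.1 do not cover them.
- *The direction is not known.* This stands. Section 9.1 expects intervention hospitals to become better at collecting clinical data, which would raise their apparent hemorrhage rate.
- *The rejection rates apply only to the follow-up t-test.* This stands too. Section 10.5 also compares baseline-to-follow-up ratios, and blood loss is measured in Periods I and III. A stable c cancels in such a ratio; only a change in c that differs by arm remains.

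A reader might infer that every woman whose collection ended early is counted as having no hemorrhage. The definition does not do that: a woman already above 500 ml when collection ends is a case. A reader might also infer that the arms will in fact differ in completeness. Nothing in the protocol shows this.

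**Conclusion.** The definition should be changed. As written, it reports true rate × share measured when missingness is unrelated to bleeding, so a 15% rate becomes 13.5% with 10% unmeasured. The loss is larger if hemorrhages are over-represented among unmeasured women. The open collection time removes further cases, by an amount the protocol's figures do not allow one to estimate.

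Bias between arms is conditional. It needs a difference by arm in completeness or collection time and can go either way. Under the assumed gaps of 10 to 20 percentage points in completeness, the spurious shift is 1.5 to 3.0 points, against planned reductions of 5 to 7 points. The matching rejection rates of about 9% to 29% hold only for the unadjusted follow-up comparison with the SD kept at 5%.

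This is a secondary outcome; the primary outcomes, episiotomy and oxytocin use, are not affected. It is worth correcting because the change is small and the outcome carries the claim of health benefit.

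**What to change.** 1. In section 5.5.2.1, make the denominator single vaginal deliveries with a recorded drape weight, and align section 2.4.1. This removes the built-in understatement when missingness is unrelated to bleeding.
2. Report the unmeasured share by hospital, arm and data collection period (I and III). Missing-data rates by hospital are already planned after each period.
3. Tabulate collection duration by arm from the start and finish times that section 5.4.1 already records.
4. Add a sensitivity analysis that applies a range of assumed hemorrhage rates to unmeasured women, allowed to differ by arm, using c × p + (1 − c) × r. Step 1 alone does not cure missingness related to bleeding.

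Do not count every woman moved from the bed as a hemorrhage. That would add false cases and rest on an unblinded judgment.

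The cost is wording in two sections, a slightly smaller denominator and one extra analysis. No new data are needed. While editing, reconcile section 5.1.1, which puts blood loss on CLIN1 and ALTA1, with section 9.1, which puts it on CLIN2.

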#### 5.5.2.2. Other secondary outcome

Provider's readiness to change with respect to episiotomies and management of third stage of labor.

### ***5.6. Process Evaluation Measures***

The objectives of the process evaluation are to

- allow early detection of implementation problems so that they can be corrected;
- detect implementation problems that could be causal, in case of no effect; and
- facilitate the replication of the intervention, in case of being effective.

We will consider process measures within three categories:

- Program inputs
- Implementation activities
- Stakeholders reactions

A provisional list of outcome measures is shown in the Table 5. This list could be modified after the refinement of the intervention.

**Table 5.** Process measures.

Process Outcome	Data needed	Intervention phase	Data collection method
Program Inputs			
Availability of information technologies resources for staff	Place, accessibility to computer by all staff	Implementation	Data Form 1 (Proc 1). One by hospital. Managed by data supervisors
Implementation Activities			
Attendance of presentation seminar	Name of attendants. List of hospital professional staff	Presentation	Special data form. One data form by hospital. Collected by data supervisors
Opinion leaders' team composition	Nº of and category of professionals	Selection of opinion leaders' team	Special data form. One data form by hospital. Collected by data supervisors
Attendance of workshops	Nº of attendants and composition, Nº and composition of team	Workshops	Special data collection form. Managed by data supervisors.
Attendance of dissemination in-hospital activities (seminar and personal visits)	Name of attendants. List of hospital professional staff	Dissemination	Special data form. One data form by hospital. Collected by data supervisors
Implementation activities below minimum (see 4.6)	Nº of monitoring reports (episiotomy rates and active management) Use of reminders Use of active management packages	Implementation	Outlook type software to register activities. Automatically/by hand by hospital coordinator
Web portal use	Web site visits E-mail consultations Participation in discussion forums	Implementation and maintenance	Automatic data collection through the software and website
Stakeholders reactions			
Knowledge acquired, attitudes to developed guidelines, opinion about selective episiotomy and active management, satisfaction with workshop	Knowledge of Evidence-Based Medicine (EBM), critical appraisal, opinion about guidelines, satisfaction with workshop (objectives accomplished, materials)	Workshops	Pre and post workshop test (knowledge) Specific questionnaires to evaluate attitudes to guidelines). Questionnaire to evaluate satisfaction. One per participant.

## **6. Training Study Personnel in Data Collection**

---

The training will be done during the preparatory phase, among other activities. This phase will take approximately 18 months. The Data Manager will coordinate the training in data collection procedures. The pilot of the manual of operations for data collection and data collection forms will be done in one hospital in Montevideo, Uruguay, and one hospital in Buenos Aires, Argentina. Those hospitals will not be randomized, but will be similar to those that will be assigned to the intervention and control group.

### ***6.1. Job Descriptions of Study Personnel***

The data collection system will be centrally coordinated at CLAP by a statistician. The team at CLAP will include one programmer, one statistical assistant and two data clerks. The computer programmer at CLAP will develop the software for data collection and validation. The statistical assistant will carry out day to day data management activities (communication with data supervisor and data clerks at the hospitals, production of monitoring and validation reports, etc). For paper forms sent to CLAP, the two data clerks will perform two independent data entries.

Two data supervisors in Argentina and one data supervisor in Uruguay will implement and supervise the data collection at the country level throughout the study period. Data supervisors will visit hospitals usually on a weekly basis, although the frequency of visits may vary according to hospital performance and needs. They will be nurses or midwives working part-time for the study. They will have expertise in clinical research and data management in collaborative trials.

There will be one in-hospital data collector in each hospital. In most cases, this personnel will be one hospital employee that will work part-time for the project. Usually an administrative that is responsible for data entry in the hospital. They will carry out data entry and validation at the hospital level.

### ***6.2. Training of Recruiters***

Not applicable.

### ***6.3. Training of Biological Sample Collectors***

Nurses or midwives in the labor ward of each hospital will be trained in how to measure total blood loss in vaginal deliveries. They will be trained to perform this measurement as a routine activity in all vaginal deliveries during the data collection periods. Data supervisors and Country coordinators will be in charge of the training activities and will provide hospitals with the standard measuring drapes.

#### ***6.4. Training of Process Evaluation Personnel***

*Intervention hospitals data clerk* will be trained to enter data in PIS, although the people usually responsible for PIS data entry will be the intended personnel for this task. Also the data clerk will keep a logbook including the date the feedback reports were distributed and the date, place, objectives, and number of participants in meetings where health providers discussed the guidelines.

#### ***6.5. Training Materials***

The manual of operations for data collection and the data collection forms will be the main training material and will be developed and tested during the preparatory phase.

#### ***6.6. Certification of Recruiters, Interviewers, Biological Sample Collectors, Laboratory and Process Evaluation Personnel***

Data supervisors in Uruguay and Argentina will be trained and certified at CLAP headquarters. Data collection and data management at the hospital level will be performed by hospital personnel that will be hired part-time by the study. These personnel will be trained by the data supervisors, and they will have to pass a standardized certification procedure before the beginning of the data collection. The data supervisors will apply the certification procedures. The certification procedure will be developed at CLAP in collaboration with the UNC-CH biostatistician. In order to be certified, these personnel will need to demonstrate a good working knowledge of the data management system (DMS) developed for the study, including procedures to assure data quality and patients' confidentiality. These personnel will also be trained in ethical issues in research with human subjects and will go through the online web training provided by the Office for Human Research Protection (OHRP), U.S. Department of Health and Human Service.

#### ***6.7. Maintenance of Training and Certification***

During the study, the DMS will produce weekly reports to monitor data quality, by hospital, in order to identify problems in particular sites. If a hospital does not fulfill the quality standards the data supervisor will increase the frequency of the visits to this site and eventually retrain the data collector. All data collectors and data supervisors will have to pass a recertification exam each year. The hospital data manager will be assessed by the data supervisors. Data supervisors will be assessed at CLAP headquarters.

## **7. Training Study Personnel in Intervention Delivery**

---

As for data collection procedures, the training in intervention delivery will be done during the preparatory phase. This phase will take approximately 18 months. CLAP study coordinator will coordinate this training. The pilot of the manual for the intervention will be done in the same pilot hospitals in Argentina and Uruguay. Those hospitals will not be randomized but will be similar to those that will be assigned to the intervention or control group.

### ***7.1. Job Descriptions of Study Personnel***

#### ***Research Associates***

They will act as country coordinators in each study site (Province of Buenos Aires, Rosario and Montevideo). They will be in charge of the daily management of the trial in each site, will be the main contact person of the opinion leader's team with CLAP study coordination, and will actively participate in the workshops as tutors. The amount of daily work is estimated to be, on average, a 50% dedication to coordinate 4 hospitals in Rosario or Montevideo and 75% to coordinate 10 hospitals in Buenos Aires Province. Qualifications for these positions include being obstetricians, being respected by their peers, have training in Epidemiology or evidence-based medicine, and have experience working as tutors in evidence-based medicine or guideline development workshops.

#### ***Trainers***

They will participate as tutors in the guideline development workshops. Each workshop will have at least two tutors and the Buenos Aires workshop will need three tutors (five hospitals, four participants in each one). The qualifications for these positions are to be health professionals (MD, epidemiologists) with previous experience in conducting evidence-based medicine or guideline development workshops.

